This is an open-label randomized controlled trial in which participants will be randomized to receive either nifedipine or enalapril in the postpartum period for hypertension requiring antihypertensives. Women who are pregnant or recently postpartum (within 6 weeks) with hypertension can be recruited for the study. They must also be at least 18 years old and planning to follow-up at Brigham and Women’s Hospital. They can be on no more than one antihypertensive and if they are, it must have been started in pregnancy. Women are not eligible for the study if they have any strict contraindications to nifedipine, enalapril or labetalol or a history of failed treatment with any of those agents. Their creatinine during admission must be less than 1.5. There will be 45 women recruited to each arm for a total of 90 women in the study. They will officially enter the trial once they are postpartum and their provider wants them to start or continue an antihypertensive.

All women will be enrolled by physician investigators or other physicians at Brigham and Women’s Hospital who have agreed to help consent patients for this study. All patients will give written consent and will be informed that a licensed physician investigator is available to speak with them at any time during the consent process.

Briefly describe study procedures. Include any local site restrictions, for example, “Subjects enrolled at Partners will not participate in the pharmacokinetic portion of the study.” Describe study endpoints.

Patients who participate in the study will be randomized to receive nifedipine or enalapril in the postpartum period to control hypertension. The assigned antihypertensive should be titrated to control blood pressure so that systolic blood pressure is consistently less than 150 mmHg and diastolic blood pressure is consistently less than 95 mmHg. If a patient reaches 90mg daily of nifedipine or 40mg daily of enalapril without achieving this blood pressure goal or the patient’s provider believes the assigned agent (nifedipine or enalapril) is ineffective, labetalol 200mg twice daily should be added to the regimen. Patients will follow-up in clinic in one week after discharge and six weeks for blood pressure checks and to have basic metabolic panels drawn.

At the six week visit, patients will be asked to complete a short survey. These are standard visits for postpartum patients. The study will be over once the patient has had her six-week postpartum visit.

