The patient may be contacted via telephone by study staff to verify any additional interactions with outside hospitals or medical providers (which would influence the primary outcome).

For studies involving treatment or diagnosis, provide information about standard of care at Partners (e.g., BWH, MGH) and indicate how the study procedures differ from standard care. Provide information on available alternative treatments, procedures, or methods of diagnosis.

There is no consensus on the best antihypertensive to use during the postpartum period. Currently at BWH, providers usually choose to use nifedipine, enalapril and/or labetalol to control postpartum hypertension as they are effective and safe during breastfeeding. The study procedures differ from standard care only in that it is formally randomized and not provider dependent.

There are alternative antihypertensives to use such as methyldopa or clonidine but these are rarely used at BWH.

Describe how risks to subjects are minimized, for example, by using procedures which are consistent with sound research design and which do not unnecessarily expose subjects to risk or by using procedures already being performed on the subject for diagnostic or treatment purposes.

Risks to participants are minimized because the protocol is not deviating from standard care as we are giving medications that we would normally give in the postpartum period.

Describe explicitly the methods for ensuring the safety of subjects. Provide objective criteria for removing a subject from the study, for example, objective criteria for worsening disease/lack of improvement and/or unacceptable adverse events. The inclusion of objective drop criteria is especially important in studies designed with placebo control groups.

Patients will be monitored closely in the hospital and then in the postpartum period. We will monitor their vital signs and any symptoms or side effects they may have. We would remove a patient from the study if she has an adverse reaction to any of the antihypertensives such as significant hypotension, uncontrollable hypertension or intolerance of the medication. We will follow-up with these patients one week after they are discharged from their hospitalization and at six weeks postpartum.

FORESEEABLE RISKS AND DISCOMFORTS

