Patients will be consented on Labor and Delivery or during an inpatient admission for antepartum or postpartum care by the physician investigators. If a patient is still pregnant, she may consent to the study and will not formally be randomized until she is postpartum and her provider determines she needs an antihypertensive. If a patient is postpartum when she is consented, her provider may want to start antihypertensives shortly after she has been consented to the study. Therefore, pregnant patients may have several hours or days to decide if they want to participate in the study. Postpartum patients will likely have less than 1 hour to decide if they want to be in the study if their provider wants to start antihypertensives as it would be unsafe to delay treatment.

If a patient is approached to be in the trial by her own provider, there will be additional objective providers available from the inpatient Maternal Fetal Medicine team to talk with the potential participant about the study.

NOTE: When subjects are unable to give consent due to age (minors) or impaired decision-making capacity, complete the forms for Research Involving Children as Subjects of Research and/or Research Involving Individuals with Impaired Decision-making Capacity, available on the New Submissions page on the PHRC website:

<https://partnershealthcare.sharepoint.com/sites/phrmApply/aicipa/irb>

For guidance, refer to the following Partners policy:

Informed Consent of Research Subjects:

<https://www.partners.org/Assets/Documents/Medical-Research/Clinical-Research/Informed-Consent-of-Research-Subjects.pdf>

DATA AND SAFETY MONITORING

Describe the plan for monitoring the data to ensure the safety of subjects. The plan should include a brief description of (1) the safety and/or efficacy data that will be reviewed; (2) the planned frequency of review; and (3) who will be responsible for this review and for determining whether the research should be altered or stopped. Include a brief description of any stopping rules for the study, when appropriate. Depending upon the risk, size and complexity of the study, the investigator, an expert group, an independent Data and Safety Monitoring Board (DSMB) or others might be assigned primary responsibility for this monitoring activity.

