Study Title: Randomized Controlled Trial Comparing Nifedipine and Enalapril in Medical Resources Used in the Postpartum Period

NCT04236258

1/3/2022

Biostatistical analysis:

The primary outcome is a composite of additional medical resources used in the postpartum period in order to control hypertension and/or the symptoms associated with the antihypertensives. The composite includes prolonged hospitalization beyond the typical stay (>2 days for a vaginal delivery, >4 days for a cesarean delivery), unscheduled clinic visits, Labor and Delivery triage visits or a postpartum readmission. The primary outcome is binary; if a patient has at least one of the composite outcomes she is considered to have the primary outcome. The secondary outcomes will include time to sustained blood pressure control (hours from initiation of medication to no additional changes to regimen), need to add additional antihypertensives (yes/no), clinically significant episodes of hyper- or hypotension (yes/no), creatinine levels at one week after discharge and six weeks postpartum, continued need for antihypertensives one week after discharge and six weeks postpartum (yes/no), side effects (listed), adverse events (listed), patient reported compliance (yes/no) and a patient satisfaction survey administered on the day of discharge from the delivery admission. The appointments at one week after discharge and six weeks postpartum are standard practice.

We plan to analyze this trial on an intention-to-treat basis. The primary outcome will be measured as the proportion of patients within each group that had at least one of the composite outcomes. To determine the baseline rate of our primary outcome, we looked at a small sample of randomly selected patients with postpartum hypertension who were discharged home on antihypertensives and observed the primary outcome occurs 70% of the time in this cohort. We believe that a clinically relevant decrease in this outcome would be to decrease this proportion below 50%. Therefore, we have chosen 40% as our target for what we would consider a successful intervention. For sample size, we are assuming an alpha of 0.05 and a power of 80%. Using a two-sided T-test in R comparing proportions of the two outcomes, we determined we will need 40 participants in each arm. Accounting for possible lack of follow-up, we will aim to enroll 45 in each arm, for a total of 90 patients.

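### Women may enter on an antihypertensive started in pregnancy, but entry treatment is neither stratified nor adjusted for, and the time-to-control clock has no common start for those already on a study drug

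*Protocol*

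**What the plan says.** The Protocol, Research Design and Methods, sets three conditions that bear on this point.

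- Prior treatment: "They can be on no more than one antihypertensive and if they are, it must have been started in pregnancy". The agent is not named.
- Prior failure: women are excluded for contraindications to nifedipine, enalapril or labetalol, "or a history of failed treatment with any of those agents".
- Entry: "They will officially enter the trial once they are postpartum and their provider wants them to start or continue an antihypertensive".

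Consent Procedures places randomisation after delivery: a woman who consents while pregnant "will not formally be randomized until she is postpartum and her provider determines she needs an antihypertensive". Recruitment Procedures describes entry as the point at which an antihypertensive is needed and does not mention continuing one.

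The arms are nifedipine and enalapril, open label. Labetalol is the named add-on if the assigned drug does not achieve control. The standard-of-care text says that "providers usually choose to use nifedipine, enalapril and/or labetalol to control postpartum hypertension".

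The SAP, Biostatistical analysis, specifies intention-to-treat and a binary composite primary outcome. Its secondary outcomes include "time to sustained blood pressure control (hours from initiation of medication to no additional changes to regimen" and a yes/no outcome for adding further antihypertensives. Neither document mentions stratification, adjustment or a subgroup by entry treatment, or says whether an entry drug that was not assigned is stopped or kept.

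**The concern.** The aim is to learn whether enalapril or nifedipine serves better as the primary postpartum antihypertensive. For an untreated woman, randomisation compares two new starts. For a woman already on nifedipine, it compares carrying on with a drug that she has not failed against receiving a different one, and the reverse holds for entry on enalapril. These are different contrasts, and one overall risk difference averages them in unknown proportions. Entry treatment plausibly predicts the outcome and modifies the effect, and it is known before randomisation, yet the plan does not use it.

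The time-to-control outcome raises a separate problem. A pregnancy-started drug always predates randomisation. Counting from the start of medication can therefore give women with the same entry drug different time origins according to the arm they are assigned to.

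**Working it through.** **1. The plan's own figure.** Inputs from the SAP: 70% versus 40%, two-sided alpha 0.05, power 80%. The unpooled normal approximation gives

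n = (1.960 + 0.842)² × (0.7×0.3 + 0.4×0.6) / 0.3² = 39.2, rounded up to 40 per arm.

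The stated 40 is reproduced, and 45 enrolled allows for 1 − 40/45 = 11.1% loss. This point disputes no number in the plan.

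**2. What each arm means, by entry treatment.**

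| At entry | Assigned nifedipine | Assigned enalapril |
|---|---|---|
| None | new start | new start |
| Nifedipine | continues | different drug |
| Enalapril | different drug | continues |
| Labetalol or other | new start | new start |

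Only the two middle rows have the continue-versus-change contrast. Whether the earlier drug is dropped or kept is not stated.

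**3. The clock.** Illustrative assumptions: nifedipine begun 21 days before delivery, randomisation at delivery, and one regimen change 24 hours later.

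| Reading of time zero | Assigned nifedipine | Assigned enalapril |
|---|---|---|
| Start of the assigned drug (literal) | 21×24 + 24 = 528 h | 24 h |
| First antihypertensive ever | 528 h | 528 h |
| Randomisation | 24 h | 24 h |

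With no regimen change after randomisation, the continuing woman scores about 0 hours on the last reading.

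On the literal reading, if a share f of the nifedipine arm entered on nifedipine with H hours of earlier use, that arm's mean is lengthened by f × H. For one day (H = 24) this is 2.4, 7.2 and 12 hours at f = 10, 30 and 50%. For seven days (H = 168) it is 16.8, 50.4 and 84 hours.

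**4. Primary outcome, illustration only.** The documents do not give f. Suppose prior nifedipine users have 70% events in both arms and everyone else has 70% versus 40%. The overall difference is then 30(1 − f) points. Power at 40 per arm, by the pooled-variance formula:

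| f | Difference, no effect in prior users | Power | Power if half the effect |
|---|---|---|---|
| 0% | 30 points | 78% | 78% |
| 10% | 27 points | 69% | 74% |
| 20% | 24 points | 59% | 69% |
| 30% | 21 points | 48% | 64% |

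**5. Chance imbalance.** At 45 per arm, the SD of the between-arm difference in f is √(2f(1 − f)/45). At f = 10% this is 6.3 points (95% range about ±12); at f = 30% it is 9.7 points (about ±19).

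**The case against.** The strongest reply is that including women whose treatment is being continued is deliberate and pragmatic. The entry wording, "their provider wants them to start or continue an antihypertensive", says so. Comparing assigned strategies in that mixed population is a legitimate question, and randomisation protects it. Chance imbalance arises for any unstratified covariate, and the test already allows for it. All of this stands, and it is why the loss is one of precision and interpretability.

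The reply also limits several stronger readings that a reader might infer:

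- **All treated entrants face continuing versus switching.** This holds only for entry on nifedipine or enalapril. Switching itself is an inference, because no text says that the earlier drug is stopped.
- **The clock starts early in one arm only.** That is true within an entry-drug group on the literal reading. If both study drugs occur at entry, early clocks occur in both arms. The SAP may have meant the first dose after entry. Time zero is undefined for these women; it is not shown to be defined wrongly. The primary outcome has no time origin and is untouched.
- **The result is pulled towards whichever drug is used more in pregnancy.** The documents describe only postpartum use, and no history of failure is not the same as being controlled.
- **The dilution figures measure a real loss.** The SAP's 70% came from women discharged on antihypertensives, with no restriction to new starters, so it may already include continuing women. Diluting it again may double count.
- **Entry on labetalol makes the add-on outcome met at entry or impossible to meet.** That requires labetalol to be kept, which is not stated. A drug already in use is not an added one, and the Foreseeable Risks text lets providers add other agents.

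**Conclusion.** The point holds as a worthwhile, inexpensive improvement. Two gaps are established from the text: a pre-randomisation factor that changes what the arms compare is left out of both randomisation and analysis, and time to control lacks a usable origin for women already on a study drug. For those women the ambiguity can be large (528 versus 24 hours under the assumed three-week exposure). For the trial as a whole, its size depends on an entry share that the documents do not give.

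The conclusion rests on the judgement that entry treatment is likely to be prognostic and to modify the effect. A reader might go further and infer that the primary comparison is confounded or the sample size wrong. Neither follows: allocation is random, analysis is by intention to treat, and the 40 per arm reproduces. No change in N is called for without a documented entry share and effect in that group.

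**What to change.** 1. **Time to control.** Measure it from randomisation in both arms and report it by entry treatment. State in advance that a continuing woman with no regimen change scores about 0 hours. This origin can favour the continuing arm, which is why the breakdown is needed.
2. **Entry treatment.** Record the agent at entry and classify it as none, nifedipine or other. Stratify randomisation by it. If randomisation has begun, use a Mantel-Haenszel stratified risk difference for the primary outcome. Any entrant on enalapril falls in the third class but stays identifiable from the recorded agent.
3. **New starters.** Give their estimate as a supportive subgroup, not the headline result. Making it the headline would change the question and lose power: at an assumed f = 30%, 0.7 × 40 = 28 evaluable women per arm remain, with about 62–66% power for 70% versus 40% (pooled and unpooled formulas).
4. **Additional antihypertensives.** Count only agents added after randomisation. The eligibility text on entry treatment and the labetalol add-on step must be reconciled, including what happens to an entry drug that was not assigned. That clinical choice is for the investigators.

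The cost is a few lines of SAP text and at most one stratification field. The eligibility check already has to establish prior treatment. With 90 women some strata will be sparse, and a stratum with an empty arm contributes nothing to the Mantel-Haenszel estimate.

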Study Title: Randomized Controlled Trial Comparing Nifedipine and Enalapril in Medical Resources Used in the Postpartum Period

NCT04236258

1/3/2022

Biostatistical analysis:

The primary outcome is a composite of additional medical resources used in the postpartum period in order to control hypertension and/or the symptoms associated with the antihypertensives. The composite includes prolonged hospitalization beyond the typical stay (>2 days for a vaginal delivery, >4 days for a cesarean delivery), unscheduled clinic visits, Labor and Delivery triage visits or a postpartum readmission. The primary outcome is binary; if a patient has at least one of the composite outcomes she is considered to have the primary outcome. The secondary outcomes will include time to sustained blood pressure control (hours from initiation of medication to no additional changes to regimen), need to add additional antihypertensives (yes/no), clinically significant episodes of hyper- or hypotension (yes/no), creatinine levels at one week after discharge and six weeks postpartum, continued need for antihypertensives one week after discharge and six weeks postpartum (yes/no), side effects (listed), adverse events (listed), patient reported compliance (yes/no) and a patient satisfaction survey administered on the day of discharge from the delivery admission. The appointments at one week after discharge and six weeks postpartum are standard practice.

We plan to analyze this trial on an intention-to-treat basis. The primary outcome will be measured as the proportion of patients within each group that had at least one of the composite outcomes. To determine the baseline rate of our primary outcome, we looked at a small sample of randomly selected patients with postpartum hypertension who were discharged home on antihypertensives and observed the primary outcome occurs 70% of the time in this cohort. We believe that a clinically relevant decrease in this outcome would be to decrease this proportion below 50%. Therefore, we have chosen 40% as our target for what we would consider a successful intervention. For sample size, we are assuming an alpha of 0.05 and a power of 80%. Using a two-sided T-test in R comparing proportions of the two outcomes, we determined we will need 40 participants in each arm. Accounting for possible lack of follow-up, we will aim to enroll 45 in each arm, for a total of 90 patients.

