**PARTNERS HUMAN RESEARCH COMMITTEE
PROTOCOL SUMMARY**

Answer all questions accurately and completely in order to provide the PHRC with the relevant information to assess the risk-benefit ratio for the study. Do not leave sections blank.

PRINCIPAL/OVERALL INVESTIGATOR

[name], PhD

PROTOCOL TITLE

A Randomized Controlled Trial Comparing Nifedipine and Enalapril in Medical Resources Used in the Postpartum Period

FUNDING

None

VERSION DATE

2/3/21

SPECIFIC AIMS

Concisely state the objectives of the study and the hypothesis being tested.

This project aims to determine if enalapril is superior to nifedipine at preventing prolonged hospitalizations, unplanned medical visits and/or readmissions in women with hypertension in the postpartum period. Our hypothesis is that women with hypertensive disorders of pregnancy randomized to enalapril as their primary antihypertensive will require fewer resources in the postpartum period than women randomized to nifedipine.

BACKGROUND AND SIGNIFICANCE

Provide a brief paragraph summarizing prior experience important for understanding the proposed study and procedures.

Hypertension is a common complication of pregnancy and the postpartum period and is responsible for a significant use of medical resources as women often require prolonged hospitalizations, unscheduled clinic visits and readmissions to control their blood pressure. (Stevens 2012, Clapp 2016) Many women may require antihypertensives to control it. Currently, at Brigham and Women's Hospital, we interchangeably use nifedipine, enalapril and/or labetalol to control postpartum hypertension. We do not know which medication is best, especially at preventing the use of extra medical resources. Nifedipine and enalapril are dosed daily so likely patients are more able to comply with treatment. We theorize that the mechanism of

action of enalapril is best suited for patients with hypertension in pregnancy as there appears to be a dysregulation of the renin-angiotensin-system. (Gant 1973)

RESEARCH DESIGN AND METHODS

Briefly describe study design and anticipated enrollment, i.e., number of subjects to be enrolled by researchers study-wide and by Partners researchers. Provide a brief summary of the eligibility criteria (for example, age range, gender, medical condition). Include any local site restrictions, for example, “Enrollment at Partners will be limited to adults although the sponsor’s protocol is open to both children and adults.”

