Provide a brief description of any foreseeable risks and discomforts to subjects. Include those related to drugs/devices/procedures being studied and/or administered/Performed solely for research purposes. In addition, include psychosocial risks, and risks related to privacy and confidentiality. When applicable, describe risks to a developing fetus or nursing infant.

There is always the risk that the antihypertensive to which a participant is randomized will not work to control blood pressure or cause side effects.

We think there is minimal risk to our trial because these are all medications we routinely use in the postpartum period. We plan to carefully monitor patient's blood pressures and symptoms and providers will be able to titrate the antihypertensives and add additional antihypertensives if needed to control blood pressure.

EXPECTED BENEFITS

Describe both the expected benefits to individual subjects participating in the research and the importance of the knowledge that may reasonably be expected to result from the study. Provide a brief, realistic summary of potential benefits to subjects, for example, "It is hoped that the treatment will result in a partial reduction in tumor size in at least 25% of the enrolled subjects." Indicate how the results of the study will benefit future patients with the disease/condition being studied and/or society, e.g., through increased knowledge of human physiology or behavior, improved safety, or technological advances.

Because this study is a randomized controlled trial, there is no direct benefit to individuals. Given the nature of the study we do not know if, and which treatment is better. Furthermore, the study is randomly allocated so there is an equal chance of the patient being in either treatment arm. However, it is hoped that prescribing enalapril for postpartum women will decrease the frequency that women have prolonged hospitalizations, unscheduled clinic visits, triage visits or readmissions in the postpartum period by 30 percentage points.

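### The primary composite counts only hypertension- or drug-related resource use, but the reason is judged in an open-label trial and no attribution-free analysis is planned

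*SAP*

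**What the plan says.** The SAP (Biostatistical analysis) defines the primary outcome as additional postpartum resources used "in order to control hypertension and/or the symptoms associated with the antihypertensives". It then lists the components: "prolonged hospitalization beyond the typical stay (>2 days for a vaginal delivery, >4 days for a cesarean delivery"), plus "unscheduled clinic visits, Labor and Delivery triage visits or a postpartum readmission". The outcome is binary: "if a patient has at least one of the composite outcomes she is considered to have the primary outcome". The list and the event rule do not repeat the cause.

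The protocol has no formal definition of the primary endpoint. Specific Aims speaks of "preventing prolonged hospitalizations, unplanned medical visits and/or readmissions in women with hypertension in the postpartum period". Expected Benefits hopes to reduce "prolonged hospitalizations, unscheduled clinic visits, triage visits or readmissions in the postpartum period by 30 percentage points". Neither statement gives a cause. Research Design and Methods allows staff to telephone patients "to verify any additional interactions with outside hospitals or medical providers (which would influence the primary outcome"). Background and Significance does link this kind of resource use to blood pressure control.

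Research Design and Methods also states: "This is an open-label randomized controlled trial". Neither document says who decides whether a stay or contact was for hypertension or drug symptoms, by what criteria, or whether that person is blind to arm. No any-cause version of the composite is planned.

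**The concern.** A stay beyond the cut-off can have a neonatal, wound or social reason, or several reasons at once. The same holds for a triage visit or readmission. Under the SAP's opening sentence such an event does not count unless it was for hypertension or drug symptoms. Under the component list read alone, it does. Someone has to decide case by case, and that person may know which drug the woman received.

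This is the only primary outcome, and at 40 evaluable women per arm a few reclassified women can change the conclusion. If attribution leans even modestly by arm, a difference can appear where resource use does not differ. A reader of the final report could not tell, because the plan contains no result free of that judgement.

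**Working it through.** **1. The plan's own figure.** SAP inputs: 70% vs 40%, two-sided alpha 0.05, power 80%. Unpooled normal formula: n = (1.960 + 0.842)² × (0.70×0.30 + 0.40×0.60) / 0.30² = 7.85 × 0.45 / 0.09 = 39.2, so 40 per arm. The pooled formula gives 42. The stated 40 reproduces, and 40/0.90 = 44.4 gives 45 if 10% loss is assumed. The point does not rest on an arithmetic error.

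**2. The wording side by side.**

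| Place | Cause stated? |
|---|---|
| SAP, opening definition | Yes: hypertension or drug symptoms |
| SAP, component list and event rule | No |
| Protocol, Specific Aims | No |
| Protocol, Expected Benefits | No |
| Protocol, Background and Significance | Yes, but not as an endpoint definition |
| Either document: who attributes, criteria, blinding | Not stated |

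**3. Illustration: lean in attribution when the drugs do not differ.** Assumption: any-cause use is 70% in both arms, and 90% of it is attributed on nifedipine. Rates counted as events are 0.70×0.90 = 63% on nifedipine, against 63%, 0.70×0.80 = 56% or 0.70×0.70 = 49% on enalapril. Rejection rates come from full enumeration of two binomials, two-sided uncorrected chi-square, 45 per arm.

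| Attributed, nifedipine / enalapril | Counted rates | Rejects |
|---|---|---|
| 90% / 90% | 63% vs 63% | 5.1% |
| 90% / 80% | 63% vs 56% | 10.0% |
| 90% / 70% | 63% vs 49% | 25.6% |

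**4. Illustration: dilution in the any-cause composite.** Assumption: 70% and 40% are related-event rates, and a share b of women in each arm has an unrelated qualifying event, independent of related ones. Any-cause rate = 1 − (1 − p)(1 − b). For b = 10%: 1 − 0.30×0.90 = 73% and 1 − 0.60×0.90 = 46%. Power is by the same enumeration.

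| b | Any-cause rates | Difference | Power, 40 per arm | Power, 45 per arm |
|---|---|---|---|---|
| 0 | 70 vs 40 | 30 | 79.6% | 81.8% |
| 10% | 73 vs 46 | 27 | 71.1% | 74.8% |
| 20% | 76 vs 52 | 24 | 61.5% | 67.6% |
| 30% | 79 vs 58 | 21 | 52.5% | 59.3% |

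At b = 20% and 45 per arm, the 95% CI half-width is 1.96 × √[(0.76×0.24 + 0.52×0.48)/45] = 19 points around a difference of 24.

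**5. Why the source of the 70% matters.** Suppose instead that the 70% was counted without regard to cause. The related rate is then 1 − 0.30/(1 − b). With the plan's relative reduction (40/70) this gives 66.7% vs 38.1%, 62.5% vs 35.7% and 57.1% vs 32.7% for b = 10%, 20% and 30%. Normal-approximation power at 40 per arm is 73%, 68% and 60%, against 78% by the same method at 70% vs 40%.

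**6. A same-direction check is too weak.** Take step 3 and call a significant result robust whenever the any-cause difference has the same sign. In 1,000,000 simulated trials, 97% (90/80 attribution) and 86% (90/70) of the false positives favouring enalapril pass. Attributed events are a subset of any-cause events, so the two results share their chance imbalance.

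**The case against.** The strongest reply is that the SAP gives one definition: the opening sentence sets the cause, and the list that follows names members of that set. That is the natural reading, and it stands. It settles which composite is primary, but it makes attribution necessary for every component and leaves it without rules.

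A reader might go further and infer that the protocol defines an all-cause endpoint that contradicts the SAP. The documents do not support this. The protocol never uses that term, it is silent on cause where it names the components, and its background agrees with the SAP. Nor does the telephone sentence make every outside contact an event. It describes how contacts are found, and a cause-restricted endpoint also has to find contacts before classifying them.

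A reader might also infer that the 70% belongs to a different definition from the 40% target. The SAP presents the 70% as the baseline rate of its primary outcome. What is unstated is only how reasons were classified in that small sample.

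Finally, the figures depend wholly on assumed rates. That is correct. Under the cause-restricted primary the dilution in step 4 does not reduce the primary power at all; it describes the sensitivity analysis.

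**Conclusion.** The concern holds in this form: a cause-restricted primary composite, in an open-label trial, with no attribution criteria and no planned analysis that avoids attribution. It should be corrected, and the correction is cheap.

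Its size cannot be derived from the documents. With no true difference, a 10- or 20-point gap in the share of events attributed would take the false-positive rate from 5% to about 10% or 26% at 45 per arm. That assumes 70% any-cause use in both arms and 90% attribution on nifedipine. These figures show sensitivity; they are not evidence that such a gap will occur. The documents also do not show that the attributor will know the arm, only that nothing prevents it. They do not support a claim that the sample size is wrong or that the two documents set rival endpoints.

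**What to change.** - **One definition.** Keep the SAP's cause-restricted composite as primary, attach the cause to each component, and word the protocol's Specific Aims and Expected Benefits to match.
- **Attribution criteria.** Write down, before data review, what makes a stay, visit or readmission count as hypertension- or drug-related, including stays with mixed reasons.
- **Any-cause sensitivity analysis.** Pre-specify the same components and cut-offs with no attribution, and report the risk difference with 95% CI beside the primary result.
- **Interpretation.** State in advance that if the primary result is significant but the any-cause difference is materially smaller or near zero, the conclusion will say that the result depends on unblinded attribution. Do not use a same-direction rule (step 6).
- **Planning rate.** State whether the 70% was counted with the cause restriction.

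The cost is a few sentences in each document and one extra analysis of data already collected. The drawback is that the any-cause estimate is diluted and less precise relative to its size. Some shrinkage (3 to 9 points in step 4) would occur without any bias, so it has to be read with its interval and not as proof of misattribution.
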